Continuous Glucose Monitor (CGM) Use in COVID-19 Patients

NCT04756141

10/15/2020

General Study Information

Principal Investigator: [name]

Study Title: Continuous Glucose Monitor (CGM) Use in COVID-19 Patients

Protocol version number and date: Ver1, 10/15/2020

Research Question and Aims

Hypothesis: CGM (continuous glucose monitor) used in the hospital in patients with COVID-19 will be as accurate as POC (point of care) glucose monitors. Provider acknowledgement CGM alarms of rapidly changing glucose trends will prevent episodes of hyper and hypoglycemia. If CGMs are found to be accurate, then their information can be used to monitor glucose level, and POC glucometer check frequency can be safely decreased to limit staff exposure to COVID19 patients and to decrease the use of personal protective equipment.

Aims, purpose, or objectives:

1. To determine if CGMs worn in the non-ICU hospital setting by patients with a diagnosis of COVID-19 and diabetes have adequate accuracy for blood glucose monitoring when compared to point-of-care capillary glucose measurement.
2. To determine if CGM use will decrease the frequency of POC (point of care) glucometer checks done in patients with COVID-19 diagnosis.
3. To determine if alerts given by CGMs worn by patients with diabetes and COVID19 would prevent episodes of hyperglycemia and hypoglycemia.

Background:

Diabetes Mellitus (DM) affects approximately 34.2 million (10.5%) Americans. Hyperglycemia and hypoglycemia in hospitalized patients have been associated with unfavorable clinical outcomes, including higher rates of sepsis, deconditioning, mortality and longer hospital stay. Untreated hypoglycemia may lead to neurological damage, cognitive decline, seizures and coma. Additionally, the management of the diabetic complications doubles the inpatient cost per capita compared to non-diabetic patients.

Currently, the hospital standard of care for glucose monitoring in diabetic patients is POC capillary blood glucose measurement performed usually before meals and at bedtime. This approach however only provides limited glucose measurements throughout the day and fails to detect nocturnal or asymptomatic hypoglycemia or hyperglycemia episodes, all of which are common insulin therapy complications. Continuous Glucose Monitors (CGM), a newly introduced technology, represent an alternative to this standard of care, with the potential to assist making personalized therapy decisions. CGMs measure and record levels of subcutaneous interstitial glucose every 5 minutes. The subcutaneous glucose measured by most recent CGMs closely mirror the capillary blood glucose levels. This continuous monitoring allows for better assessment of nocturnal or asymptomatic hypoglycemia or hyperglycemia, and shows glycemic patterns following treatment interventions. This monitoring allows for timely interventions, and was shown to reduce hyperglycemia and hypoglycemia episodes. Recent studies have demonstrated improved glycemic control in insulin-treated DM patients using

CGM in outpatient setting. FDA has approved these devices in outpatient setting for glucose monitoring and for dosing of insulin injection even without capillary blood glucose confirmation. In the outpatient setting these devices have become standard of care for both type 1 and type 2 diabetes management. Their use in inpatient setting is limited, and at this time it is not FDA approved. Concerns for reading accuracy in case of rapidly fluctuating clinical parameters, hypoxemia, tissue hypoperfusion and IV medications use have prevented the approval of these devices in inpatient setting. Still, when evaluated in hospitalized patients, small studies have found that CGMs are accurate and they can detect more episodes of hypo and hyperglycemia than POC glucometers, especially between meals and at night time.

COVID-19 pandemic has led to increase hospitalization for patients with diabetes mellitus. Current guidelines recommend treatment with high dose of steroids for COVID-19 patients requiring oxygen supplementation. This therapy leads to hyperglycemia in patients with known DM, but also in patients without previous diagnosis of diabetes. Hyperglycemia treated with insulin could lead to hypoglycemic episodes, especially in frail and very sick patients. Close monitoring of blood glucose is imperative in these patients.

The blood glucose monitoring with POC blood glucose monitors is done at bedside by nursing staff. This requires direct contact with the patient and nurse presence in the room. Depending on frequency of glucose monitoring this presence ranges from 4 times per day to every hour if patients are receiving therapy with IV insulin. Patients with COVID-19 require modified airborne isolation and nursing staff has to use PPE when entering patients' rooms.

A few pilot studies had evaluated the use of CGMs in patients with COVID19 with the aim of reducing hypo and hyperglycemia episodes and nursing staff exposure.

Manufacturers (DEXCOM and ABBOTT) are providing CGM sensors and readers to be used in COVID19 patients with the aim of decreasing the use of health care resources (PPEs) and health care providers' effort during the pandemic. Even if these sensors are not approved by FDA to be used in inpatient setting, FDA has allowed manufacturers to provide these devices to be used in COVID19 patients "to allow hospital staff to remotely monitor glucose in patients to reduce patient interaction, limiting viral exposure by hospital staff and preserving PPE."

With this study we aim to determine if CGMs are as accurate as POC glucometers, if CGM alerts can reduce episodes of hypo and hyperglycemia, and if by using CGM data to dose insulin we can decrease the number of finger-sticks and nurse exposure to COVID19 patients.

Study Design and Methods

Methods:

All patients admitted to the hospital in inpatient status with a diagnosis of COVID-19 will be screened and identified by research team. Patients meeting inclusion criteria will be approached by a research team member and will be asked to enroll. The study will be explained and informed consent will be discussed in detail. If patients agree to enroll, they will be fitted with a Dexcom G6 sensor by nursing staff as per protocol. If MRI imaging is planned, sensor placement will be deferred until after MRI is completed. The CGM will not interfere with Xrays or CT scans (sensor can be covered by a lead shield if needed). A hospitalist or IP Endocrinology staff can temporarily remove the transmitter if it will interfere with medical testing.

Diabetes educators and Endocrinology ARNPs will be available to help with the following tasks. The CGM information will be entered into receiver phone and iPad tablet present at nursing station. The receiver phone will be placed outside patient room in nursing alcove. Here it will remain available for staff to use and to respond to CGM alarms. Alarm limits for hypoglycemia and hyperglycemia will be set on the receiver phone

and on the iPad tablet at the nursing station. These alarms settings will vary depending on whether the patient is on IV insulin infusion vs. subcutaneous (SQ) insulin. The number of glucose checks required with these two types of insulin varies significantly and requires separate handling as detailed below.

Two flow-sheet protocols will be made available to nursing staff with instructions on data collection and insulin management: one for IV insulin infusion and one for SQ insulin. Nursing staff will choose the appropriate protocol at the time of CGM placement based on the type of insulin the patient is receiving. If the patient is transitioned from IV insulin to SQ insulin during the course of the study, the research team will be contacted to provide instructions on safe transition from the IV insulin protocol to the SQ insulin protocol. CGM presence will be recorded by nursing in patient chart under LDA (lines, drains, airway) section. CGM state will be monitored daily by nursing team and any evidence of localized side effects (skin lesions, pain, sensor and adhesive breakdown) will be recorded in patient's chart. Nurses will be asked to report these changes to research team. Research team will survey these recordings daily and evaluate the patients and confirm these side effects. Should these local skin reactions meet criteria for discontinuation then the sensor will be removed and patient participation in research will be terminated.

After placement, CGMs will enter the “warm up phase” for 2 hours. During this period no CGM data will be displayed and nursing staff will continue BG monitoring using Point of Care (POC) glucometer per orders. Once warm up is completed, CGMs will transmit data every 5 min to the receiver phone and their data can be recorded. Nursing staff will be asked to record CGM values in patient chart.

The use of CGMs will be divided in 2 phases – “Adjustment Phase” and “Utilization Phase”. The instructions for these phases will differ for patients on IV insulin infusion vs. SQ insulin infusion and are described in detail below.

For patients receiving subcutaneous (SQ) Insulin:

Adjustment Phase

During the first 24 hours, sensor accuracy will be assessed. Patients will continue to have their blood glucose checked with POC glucometer concomitant with CGM use. CGM readings will be recorded in chart at the same time as POC glucometer reading is obtained. The glucometer readings and CGM data at the time of glucometer readings will be compared by nursing staff. The CGM readings should not be either 15% higher or 15% lower than the corresponding POC glucometer reading. Should this CGM reading fall outside this range, a second reading will be done within 30 minutes and readings will be compared to reassess accuracy. After the patient has had sensor in place for 24 hours and at least 4 POC glucometer glucose checks have been recorded and compared against CGM values and found to fall within the above range, the research team will be notified to determine if the frequency of POC checks can be safely decreased based on CGM accuracy.

If 2 or more consecutive CGM readings do not correlate with POC glucometer values, the research team will be notified. The research team will evaluate the data and decide if the sensor should be replaced and another 24-hour cycle of adjustment phase re-initiated, or if patient participation should be terminated. Only POC glucometer readings will be used to make decision about insulin dosing and administration during this phase. When charting insulin

administration, nursing staff will manually enter the CGM readings obtained at the time of insulin administration into the chart under the “comments” on the MAR screen.

If 4 comparison points – CGM readings and POC glucometer reading – are deemed accurate (within +/- 15% of each other for all 4 readings), then patient will enter the “Utilization Phase”.

Utilization Phase

During this phase, once the research team has confirmed CGM accuracy, POC glucometer AND CGM readings will be used to make decisions about insulin dosing and administration. The use of POC glucometer will be decreased as follows:

1. POC glucometer checks will be reduced from 4 times per day (qAC and QHS) to twice per day before breakfast and at bedtime (qAM and qHS)
2. Subcutaneous insulin dose for breakfast and bedtime will be determined based on POC readings
3. Subcutaneous insulin dose for lunch and dinner will be determined based on CGM readings
4. Nursing staff will continue to record CGM readings at the time of every insulin administration in the chart under the “comments” section on the MAR
5. Nursing staff will compare AM and HS (before breakfast and at bedtime) POC glucometer reading to concomitant CGM reading to ensure readings remain accurate (within +/- 15% of each other). If CGM readings will fall outside this range, nursing will contact the research team for directions. The research team will recommend either to retest the accuracy of the sensor with POC glucometer, or to exchange the CGM sensor and then test the accuracy

The CGM will be set up with alarm limits of 85 for low glucose and 250 for high glucose. If these alarms are triggered, the nursing staff will take measures for these alarms as listed below. Treatment decisions will be made based on the POC glucometer reading as follows:

- For hypoglycemia alarm (BG<85mg/dl), POC glucometer will be used to confirm the glucose level. Measures will be taken to prevent or treat hypoglycemia.
 - If BG is 70-85mg/dl, patient will receive 15 gm of carbohydrates PO ASAP and blood glucose will be re-checked in 30 minutes.
 - If BG is <70, hypoglycemia protocol will be initiated. IV D50 pushes or IM glucagon will be used if patient is obtunded and unable to swallow. POC glucose will be re-checked in 15-30 minutes to ensure appropriate correction of hypoglycemia.
- For hyperglycemia (sustained BG>250) for more than 2 hours in a row, nursing staff will contact primary provider or inpatient endocrinology team for insulin dosing recommendations. POC glucose check will be obtained based on provider recommendations. Additional insulin will not be given between meals regardless of sensor reading unless otherwise recommended by attending physician or ARNP provider. Close attention will be given to avoid “insulin stacking phenomenon” and potential hypoglycemic events.

For patients receiving IV Insulin infusion:

Please note that during the entirety of the study while the patient is receiving IV insulin, the insulin infusion dose will only be adjusted using the POC BG readings. CGM data will only be used to monitor BG range and if BG is found to be outside of expected range, the POC glucose will be checked and insulin infusion will be adjusted based on the POC glucometer reading.

Adjustment Phase

In the “Adjustment Phase”, during the first 12 hours, sensor accuracy will be assessed. Patients will continue to have their blood glucose (BG) checked with POC glucometer concomitant with CGM use. Nursing staff will check POC BG every 1 hour for the first 12 hours (as per established IV insulin infusion protocol). CGM readings will be recorded in chart at the same time as POC glucometer reading is obtained. These readings will be entered by nursing staff under the “comments” section of the MAR screen. The glucometer readings and CGM data at the time of glucometer readings will be compared by nursing staff. The CGM readings should not be either 15% higher or 15% lower than the corresponding POC glucometer reading. Should this CGM reading fall outside this range, a second reading will be done within 30 minutes and readings will be compared to reassess accuracy. After the patient has had sensor in place for 12 hours and at least 12 POC glucometer glucose checks have been recorded and compared against CGM values, the research team will be notified to determine if the frequency of POC checks can be safely decreased based on CGM accuracy.

If 12 comparison points – CGM readings and POC glucometer reading – are deemed accurate (within +/- 15% of each other for all 12 readings), then patient will enter the “Utilization Phase”.

If 2 or more consecutive CGM readings do not correlate with POC glucometer values, the research team will be notified. The research team will evaluate the data and decide if the sensor should be replaced and another 12-hour cycle of adjustment phase re-initiated or if patient participation should be terminated.

Utilization Phase

Once CGM accuracy has been established in the “Adjustment Phase” above, the frequency of POC glucose checks will be reduced as follows:

1. POC glucometer checks will be reduced to every 2 hours
2. CGM readings will continue to be recorded hourly by nursing staff.
 - a. If CGM glucose remains in range (140-180 mg/dl), the same insulin infusion rate will be continued.
 - b. If CGM glucose is out of range (<140 or >180) then nursing staff will resume POC glucose check every 1 hour. Insulin infusion will be adjusted as needed per IV insulin infusion protocol using the POC glucometer reading **only**.
3. If IV insulin infusion dose is adjusted, nursing staff will resume POC glucometer checks every 1 hour until the POC glucose remains in range for 2 consecutive readings
4. Once BG remains within range for 2 consecutive POC glucometer readings, POC glucose checks will be again decreased to every 2 hours

5. If the patient is transitioned from IV insulin infusion to SQ insulin, the nursing staff will notify the research staff and will proceed to the SQ insulin protocol above. The alarms will be adjusted as described in the SQ insulin protocol.

The CGM will be set up with alarm limits of **Low Glucose (<140 mg/dl)**, **Urgent Low Glucose (<70)** and **High Glucose (>180)**. If these alarms are triggered, the nursing staff will perform a STAT POC glucose check to confirm blood glucose (BG) level. Treatment decisions will be made based on the POC glucometer reading as follows:

- For hypoglycemia:
 - If POC BG is between 85-140 mg/dl, hold IV insulin infusion and re-check POC glucose in 30 minutes
 - If POC BG is between 70-84 mg/dl, hold IV insulin and ask patient to take 15gm of carbohydrates PO ASAP and recheck POC glucose level in 30 minutes
 - If POC BG is < 70, apply hypoglycemia protocol. Hold IV insulin. Give IV D50 or IM glucagon to obtunded patients. Give PO carbohydrates to alert, able to swallow patients. Repeat POC glucose level in 15 min. and 30 min.
 - Continue to check POC blood glucose every 1 hour until glucose remains in range (140-180 mg/dl) for 2 consecutive readings.
 - Once BG remains within range for 2 consecutive POC glucometer readings, POC glucose checks will be decreased to every 2 hours
- For hyperglycemia (BG>180):
 - Check glucose level using POC glucometer and adjust IV insulin infusion rate accordingly
 - Continue checking POC glucose every 1 hour until glucose remains in range (140-180 mg/dl) for 2 consecutive readings
 - Once BG remains within range for 2 consecutive POC glucometer readings, POC glucose checks will be decreased to every 2 hours

Methods (continued):

Treatment of the DM and associated complications, dosing of the insulin, change from PO to insulin treatment and back to PO medications during hospitalization or at discharge will be guided by the admitting team with as needed help from the inpatient Endocrinology Consultation Service.

CGM data will be compared with POC blood glucose monitoring obtained in the hospital. Different patient variables (demographics, comorbidities, labs and vitals, administered medications) will be collected from electronic health record and will be evaluated to determine if they would interfere with CGM readings. The accuracy of CGM for glucose measurement in the hospital will be calculated.

At the time of discharge or after discharge patients will be contacted by research team and administered a survey regarding satisfaction with inpatient care and satisfaction with DM care.

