The study will use data that have been collected under another IRB protocol. Include in the Methods section and enter the IRB number from which the research material will be obtained. *When appropriate, note when subjects have provided consent for future use of their data and/or specimens as described in this protocol.*

Enter one IRB number per line, add more lines as needed

Data Specimens Data & Specimens _____

Data Specimens Data & Specimens _____

Data Specimens Data & Specimens _____

Data Analysis

Power Statement:

This a pilot study to demonstrate feasibility of CGM use in COVID patients and to determine if a subsequent more extensive implementation and studying of this device will be warranted.

Data Analysis Plan:

Data will be described as percentages or means. Pearson χ^2 and Kruskal Wallis tests will be used to compare categorical and continuous variables respectively. Odds ratios, 95% confidence intervals and p-values will be reported for each model. All tests of significance will be 2-sided and the level of statistical significance will be set at p-value < 0.05 .

Mean Absolute Relative Differences will be calculated between matched pairs of POC monitors and the closest CGM reading (within 5 minutes of POC). Additionally, level of agreement between the two devices will be examined with Bland-Altman plots, with particular attention focused on detection agreement in range (70-180 g/dl). Poisson or negative binomial regression will be utilized to assess count variables such as number of alarms, nurse notification, and hypo or hyperglycemia events adjusting for patient characteristics. Finally, longitudinal analysis will be conducted to determine differences associated with medications, clinical parameters or diagnosis. Analysis will seek to define if there are any differences between CGM and POC measurement based on these changes.

Endpoints

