**Primary:**

CGM accuracy - mean absolute relative difference (MARD)

The frequency of POC glucometer use in Adjustment and Utilization phase

Secondary:

- CGM accuracy at detection of hypo or hyperglycemia episodes when compared with POC monitors. (MARD for readings <70g/dl, >180g/dl, >250g/dl)
- CGM accuracy for detecting time in range (70-180 g/dl MARD).
- Number of CGM alarms and the clinical result of these alarms: nurse notification, treatment of hypo or hyperglycemia episodes, treatment for rapid declining glucose alarms.
- Time in therapeutic range for glucose as measured by CGM and POC glucose monitor.
- Detection of medications, clinical parameters or diagnoses that would interfere with CGM reading.
- Effect of CGM use on length of hospital stay.

Clinical safety measures:

- Patients with severe hypoglycemia episodes (POC glucose check below 50 mg/dl).
- Patients with DKA or HHS diagnoses after admission and enrollment in the study.
- Number of sensors with failure.
- Number of sensors removed for procedure.
- Number of sensor related skin reaction (contact dermatitis, infection)

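### The hypothesis claims that CGM is as accurate as POC, but with POC as the only reference the study can show agreement and cannot show which device is closer to true glucose

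*Combined protocol and SAP*

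**What the plan says.** The equal-accuracy claim appears twice in the combined protocol and SAP. The Hypothesis, under Research Question and Aims, reads "CGM (continuous glucose monitor) used in the hospital in patients with COVID-19 will be as accurate as POC (point of care) glucose monitors". The last paragraph of the Background says "With this study we aim to determine if CGMs are as accurate as POC glucometers".

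Aim 1 is worded differently. It asks whether CGMs "have adequate accuracy for blood glucose monitoring when compared to point-of-care capillary glucose measurement", which is a question of agreement with POC.

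The planned comparisons all follow Aim 1:

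- Methods (continued): "CGM data will be compared with POC blood glucose monitoring obtained in the hospital".
- Data Analysis Plan: "Mean Absolute Relative Differences will be calculated between matched pairs of POC monitors and the closest CGM reading (within 5 minutes of POC"). The same section adds that "level of agreement between the two devices will be examined with Bland-Altman plots".
- Endpoints: MARD is a primary endpoint. The secondary accuracy endpoints are MARDs by glucose range.
- Adjustment and Utilization Phases: the bedside accuracy check is ±15% against the paired POC value.

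The study takes no specimens of its own. Laboratory data enter in one place, Methods (continued): "Different patient variables (demographics, comorbidities, labs and vitals, administered medications) will be collected from electronic health record". Their stated purpose there is to look for factors that interfere with CGM readings. They are given no role as a glucose reference.

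**The concern.** To say that one device is as accurate as another, one needs the error of each against a common reference. Here one of the two devices is the reference, so the CGM-POC difference mixes both errors and any POC error is counted against CGM.

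What is at stake is the sentence the study may write at the end. The Hypothesis makes fewer POC checks depend on CGM being found accurate, and the Power Statement says the pilot will inform whether wider implementation is warranted. A low MARD could be reported as equal accuracy, which goes beyond the data. A high MARD could be put down to CGM when POC contributed part of it. The secondary endpoint on medications, clinical parameters and diagnoses that interfere with CGM has the same limit: a factor that disturbs POC would look like interference with CGM.

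**Working it through.** The plan gives no MARD target, device error, equivalence margin or power calculation, so there is no figure of its own to reproduce. The question is what a CGM-POC comparison can identify. All error sizes below are assumptions.

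**1. Closed form.** With independent, unbiased, roughly normal relative errors:

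expected CGM-POC MARD ≈ √(2/π) × √(SD(CGM)² + SD(POC)²), with √(2/π) = 0.798.

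- SDs 10% (CGM) and 5% (POC): 0.798 × √125 = 0.798 × 11.18 = 8.92%.
- SDs 5% and 10%: the same sum, so again 8.92%.
- SDs 0% and 10% (a perfect CGM): 0.798 × 10 = 7.98%.

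Against true glucose, an SD of 10% is a MARD of 7.98% and an SD of 5% is 0.798 × 5 = 3.99%. The first two cases therefore have true MARDs (CGM / POC) of 7.98 / 3.99 and 3.99 / 7.98. The ranking is reversed and the endpoint is the same.

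**2. Simulation.** One million pairs; true glucose lognormal (median 180 mg/dl, log-SD 0.3); independent multiplicative errors; MARD computed as the mean of |CGM/POC − 1|.

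| Assumed error SD, CGM / POC | CGM-POC MARD | Pairs within ±15% | True MARD, CGM / POC |
|---|---|---|---|
| 12.5% / 0% | 10.02% | 77.2% | 10.02% / 0% |
| 11% / 6% | 10.05% | 77.0% | 8.82% / 4.80% |
| 8.84% / 8.84% | 10.01% | 77.3% | 7.07% / 7.06% |
| 6% / 11% | 10.05% | 77.0% | 4.80% / 8.81% |
| 0% / 12.5% | 10.03% | 77.2% | 0% / 10.03% |

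The planned results are essentially identical in all five rows.

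**3. Bias.** Both SDs are kept at 8.84%.

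- CGM 10% high: MARD 13.88%, mean relative difference +10.84%, true MARDs 11.63 / 7.08.
- POC 9.09% low: MARD 13.88%, mean relative difference +10.85%, true MARDs 7.07 / 10.05.
- Both 10% high: MARD 10.03%, true MARDs 11.64 / 11.65.

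The first two cases cannot be told apart by MARD or by the mean difference on a Bland-Altman plot, although the less accurate device differs. The third shows that a bias shared by both devices is invisible.

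**4. What agreement does establish.** With C, P and T for CGM, POC and true glucose, the triangle inequality gives |C − T|/T − |P − T|/T ≤ |C − P|/T, and the same with C and P exchanged. On average, the gap between the two true MARDs cannot exceed the CGM-POC MARD, to first order (the plan's MARD would normally divide by P, and the bound divides by T). The five table rows fit: the gaps are 10.0, 4.0, 0.0, 4.0 and 10.0 points, against a MARD of about 10%.

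**The case against.** The strongest reply is that a reader might infer from the above that the hypothesis can be neither supported nor refuted. That goes too far. By step 4, close agreement with POC bounds the difference in accuracy, and so gives some support to equal accuracy within that bound. What is lost is the ability to rank the devices and to say which one caused a disagreement.

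Second, the operative text already asks about agreement. Aim 1, the first item under Outcomes measured and the Bland-Altman sentence are all framed against POC. POC is described as the hospital standard of care, and the practical question is whether CGM can replace some POC checks. For that question POC is a defensible comparator, and this is a 20-patient feasibility pilot. All of this stands. It places the fault in the Hypothesis and the Background aim, not in the choice of comparator. Pilot status excuses low precision, but more patients would not cure this mismatch.

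Third, a reader might infer that the protocol itself doubts POC readings in this population. The Background raises hypoxemia, hypoperfusion and IV medications as concerns about CGM only. The one POC-specific concern, edema affecting the finger-stick sample, is handled by exclusion. The documents give no evidence that POC is unreliable in the enrolled patients.

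Fourth, two-device data can separate the error variances under strong assumptions (independent errors, a common scale, no proportional bias). Even then each device's absolute bias stays unknown, and no such analysis is planned.

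**Conclusion.** The point holds as a mismatch between the stated hypothesis and the planned measures. The Hypothesis and the Background aim promise a comparison of accuracy; the analyses deliver agreement with POC. A CGM-POC MARD of about 10% is compatible with CGM being much worse than POC, equal to it or much better: true MARDs from 10 / 0 to 0 / 10 under the assumed errors. The size of those errors is assumed and does not estimate a defect in this trial. That the comparison cannot rank the devices does not depend on the particular values chosen.

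The data collection is not at fault, and Aim 1 can be addressed as designed once its standard of adequacy is given a number. The plan has none at study level; its ±15% is a per-patient check.

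**What to change.** Reword the Hypothesis and the Background aim, and commit the study conclusion to the same form: *CGM agrees with POC within a pre-stated limit*. State the limit before the data are analysed. For example, report MARD and the percentage of pairs within the plan's own ±15%, each with a confidence interval that allows for clustering of readings within patient. State that equal accuracy will not be concluded.

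Optional and supportive only: if the extracted record turns out to hold laboratory glucose values close in time to a CGM-POC pair, report the MARD of CGM against laboratory and of POC against laboratory on the same triplets. The documents do not establish that such values exist, and they set no pairing window. If there are too few, the rewording stands alone.

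The cost is a few sentences in the protocol and clustered intervals on measures already planned or directly computable from the same pairs. No patients, visits or samples are added.

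### Aim 3 and the length-of-stay endpoint ask causal questions that a single group of 20, all wearing the CGM, cannot answer; the rapid-change alarms in the hypothesis also do not match the alarms described

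*Combined protocol and SAP*

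**What the plan says.** **Causal statements.** Under Research Question and Aims, aim 3 is "To determine if alerts given by CGMs worn by patients with diabetes and COVID19 would prevent episodes of hyperglycemia and hypoglycemia". The hypothesis in the same section is firmer: "Provider acknowledgement CGM alarms of rapidly changing glucose trends will prevent episodes of hyper and hypoglycemia". The last paragraph of Background sets out to determine "if CGM alerts can reduce episodes of hypo and hyperglycemia". Endpoints (Secondary) lists length of stay as an effect of using the CGM. Outcomes measured lists it neutrally, among other hospital outcomes.

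**Design.** Methods states: "If patients agree to enroll, they will be fitted with a Dexcom G6 sensor by nursing staff as per protocol". Subject Information gives a target accrual of 20, and the Power Statement calls the study a feasibility pilot. No section describes a comparison group.

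**Alarms.** Methods says "Alarm limits for hypoglycemia and hyperglycemia will be set on the receiver phone" and on the tablet at the nursing station, and adds: "These alarms settings will vary depending on whether the patient is on IV insulin infusion vs. subcutaneous (SQ) insulin". The SQ section gives limits of 85 and 250 mg/dl. The IV section gives below 140, urgent below 70, and above 180 mg/dl. All of these are glucose levels. Outcomes measured and Endpoints nevertheless include treatment following alarms for rapidly falling glucose.

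**Analysis.** The Data Analysis Plan models alarms, nurse notifications and glycemic events by Poisson or negative binomial regression, adjusted for characteristics of the patient. It names neither exposure time nor insulin route. Methods foresees a change of route ("If the patient is transitioned from IV insulin to SQ insulin during the course of the study"), and the IV section then moves the alarms to the SQ limits.

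**The concern.** To say that alerts prevent episodes, or that the device changes length of stay, one needs an estimate of what would have happened without it. The plan describes no source for that estimate. The Data Analysis Plan sets two-sided tests at 0.05, so a p-value could come to be attached to a claim of prevention that has no counterfactual behind it.

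The alarm mismatch is a separate matter. If the hypothesis rests on rapid-change alarms, a reader of the results must know whether such alarms were switched on, and this document does not say.

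**Working it through.** The plan states no power, effect size, SD or event rate, so there is no figure to reproduce. The check sets the passages side by side, with arithmetic on stated assumptions where useful.

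**1. Is there a comparator between patients?** No. All enrolled patients are fitted with a sensor (Methods), so 0 of 20 are without one. No historical cohort is defined. The medical-records section is form text and describes no control group.

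**2. Could the Adjustment Phase be a within-patient control?** Endpoints (Primary) uses the phase contrast only for POC frequency. Whether alarms sound during Adjustment is not stated: Methods describes setting them with the device, but the actual limits and responses follow the Utilization lists. Suppose they were silent. Then:

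- *Order and time.* Adjustment always comes first, so phase is confounded with time since admission and with the course of the illness and its treatment.
- *Ascertainment.* Scheduled POC checks fall from 4 to 2 per day (SQ) and from hourly to every 2 hours (IV), while alarms add unscheduled checks. POC-based episode counts would change with no change in glucose.
- *Selection.* Entry to Utilization needs all 4 (SQ) or all 12 (IV) pairs within 15%. If each pair passes independently with probability p (assumed 0.80 to 0.95, ignoring retests and repeat cycles), the share entering is p^4 = 0.41 to 0.81 for SQ and p^12 = 0.07 to 0.54 for IV. The two phases would not contain the same patients.
- *Amount of data.* SQ: 20 × 22/24 = 18.3 patient-days, after removing the 2-hour warm-up. IV: 20 × 12/24 = 10 patient-days. With an assumed 0.1 to 0.5 episodes per patient-day and 3 to 7 Utilization days for all 20, simulated power to detect a halved rate (exact conditional test) is 5% to 35%.

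Length of stay is measured once per patient, so no phase contrast can address it at all.

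**3. Would a small added control group rescue the effect estimate?** With 20 against 20, the detectable difference at 80% power and two-sided 0.05 is (1.960 + 0.842) × √(2/20) = 0.89 SD. Detecting 0.5 SD would need 2 × 2.802² / 0.5² = 62.8, that is 63 per arm.

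**4. What can 20 patients describe?**

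- Mean length of stay: half-width t(0.975, 19)/√20 = 2.093/4.472 = 0.468 SD. For an assumed SD of 3 to 8 days this is ±1.4 to ±3.7 days.
- Episode rate: an assumed 10 episodes in 100 CGM-days gives 0.10 per day, exact Poisson 95% CI 0.048 to 0.184 before any allowance for clustering within patients.

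**5. Do raw alarm counts need exposure and route?** At a constant alarm rate, 6 days of wear gives 6/2 = 3 times the count of 2 days. Limits also differ by route and change within a patient who moves from IV to SQ, so a covariate fixed per patient cannot represent route.

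**The case against.** The strongest defense is that this is a declared feasibility pilot, that its primary endpoints (MARD and POC frequency) do not depend on aim 3, and that Outcomes measured already words length of stay neutrally. That stands as far as it goes. Pilot status excuses the absence of a power calculation. It does not excuse an aim, a hypothesis and an endpoint that the design cannot answer.

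A reader might also infer several stronger points that the documents do not support:

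- *That warm-up is the only time without alerts, giving 20 × 2 h = 40 patient-hours.* During warm-up, Methods says "During this period no CGM data will be displayed and nursing staff will continue BG monitoring". But Methods also allows temporary removal of the transmitter, and both Adjustment sections allow sensor replacement. The figure is not the total, and Adjustment may or may not be alert-free.
- *That alarm counts will be pooled across routes.* The plan does not say so. The adjustment for patient characteristics could be meant to include route, and Methods says the two insulin types need separate handling. The gap is that exposure time and route are not named.
- *That the IV limits produce several times more alarms.* Any such ratio needs glucose distributions that the documents do not give, and under plausible assumptions even its direction is open.
- *That rapid-change alarms will not be used.* Methods refers to nursing flow-sheets that are not reproduced here. Only their absence from this document is established.

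**Conclusion.** The concern holds for the causal wording. Four statements (aim 3, the matching hypothesis sentence, the closing sentence of Background and the secondary length-of-stay endpoint) claim or seek an effect that one group of 20, all wearing the device, cannot estimate. This rests on the design as written and on no numerical assumption. Phase is not a usable substitute, whatever the alarm status in Adjustment.

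The mismatch between rapid-change alarms and level-only limits is also real within this document. The missing exposure time and route in the count models is a minor clarification.

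The point should be corrected, and it leaves the two primary endpoints untouched. The power, selection and precision figures above are illustrations on assumed inputs, except the ±0.47 SD, which follows from n = 20 and the usual t interval.

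**What to change.** 1. **Restate as descriptive** aim 3, the hypothesis sentence, the closing Background sentence and the secondary length-of-stay endpoint: episode rate per monitored CGM-day and length of stay, each with a 95% confidence interval and no claim of prevention or effect. This matches the neutral wording in Outcomes measured. State the episode definition and its data source (POC or CGM); none is chosen here.
2. **Reconcile** the rapid-change hypothesis and the rapid-decline outcome with the alarms actually configured, and state which alarms are logged and whether they are active in the Adjustment Phase. No setting is proposed.
3. **Clarify the count analysis.** Report alarms and notifications per monitored CGM time (a log-time offset in the regression), separately for IV and SQ periods, splitting time at a switch and allowing for repeated periods within a patient. Where few patients are on a route, report its rates descriptively.

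**Cost.** Edits to one aim, one hypothesis sentence, one Background sentence and the affected endpoint and outcome lines, plus a few lines in the Data Analysis Plan. No patients or visits are added. The causal claim is given up, the estimates are imprecise (mean length of stay ±0.47 SD), and rates by route will be less precise than the pooled rate.
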